(Dave, 2012). In addition, endoscopic assessments at time points later than 12 weeks in placebo-controlled studies have posed the problem of limited comparative data due to the low number of placebo subjects remaining beyond the 12-week time point. Hence, the 12-week time point was selected for the endoscopic endpoint in this study.

Three active dosing regimens will be evaluated following the initial 12-week treatment with GED-0301 160 mg QD, in which two different doses (160 mg QD and 40 mg QD) and different dosing schedules (continuous and alternating) will be evaluated in order to determine dose and dosing regimen that provides the best benefit to risk for subjects with active CD.

Two doses, 160 mg QD and 40 mg QD, were selected to be evaluated after the initial 160 mg QD 12-week treatment since the 160 mg QD dose is expected to provide the highest level of efficacy, and the 40 mg QD dose is the lowest efficacious dose, which has been demonstrated in subjects with active CD [REDACTED]. This is clinically pertinent, since subjects who achieve clinical response or clinical remission after the initial 12-week treatment may require a lower dose than that initially needed for the treatment of moderate to severe CD.

Three different dosing regimens will be evaluated: one continuous dosing regimen (GED-0301 40 mg QD) and two alternating dosing regimens (GED-0301 40 mg QD for 4 weeks on/4 weeks off and GED-0301 160 mg QD for 4 weeks on/4 weeks off). Consequently, these 3 different dosing regimen strategies correspond to incremental increases of 2-fold differences between each of the 3 arms in total IP exposure during the 40-week long-term maintenance treatment. The alternating dosing regimen is supported by findings from Study [REDACTED], in which after 2 weeks of dosing, the majority of subjects had a prolonged clinical improvement up to Week 12, suggesting that patients may not need continuous dosing. This strategy may be more advantageous for longer term treatment in patients with CD, including the potential for a more favorable benefit to risk profile than a continuous dosing regimen.

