| Clinical Lab (Chemistry) g  | X                | X                             | -          | -          | X               | -          | X          | -          | X          | -          | X          | -          | X          | -          | X               | X                | X  |
| Clinical Lab (Urinalysis) g   | X                | X                             | -          | -          | X               | -          | X          | -          | X          | -          | X          | -          | X          | -          | X               | X                | X  |
| Efficacy Assessments  |                  |                               |            |            |                 |            |            |            |            |            |            |            |            |            |                 |                  |  |
| Subject Diary h
Instruct use of electronic device/assess compliance | X                | X                             | X          | X          | X               | X          | X          | X          | X          | X          | X          | X          | X          | X          | X               | X                | X  |
| CDAI i  | X i   | X                             | X          | X          | X               | X          | X          | X          | X          | X          | X          | X          | X          | X          | X               | X                | X  |
| Ileocolonoscopy j   | X                | -                             | -          | -          | X               | -          | -          | -          | -          | -          | -          | -          | -          | -          | X               | X                | -  |

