#### 5.3.3. Safety Population

The analysis of safety data in this study will be based on the safety population, which will consist of all subjects who are randomized and receive at least 1 dose of IP.

At least 1 post-baseline assessment is required for inclusion in the analysis of each specific laboratory, vital sign, weight, or ECG parameter. To assess the change from baseline, a baseline assessment is also required.

Subjects will be included in the treatment group corresponding to the IP they actually received for the analysis using the safety population.

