### 12.2.1. Overall Summary of TEAEs

An overall summary of the following TEAE categories will be provided for Weeks 0-12, Weeks 12-52, and Weeks 0-52:

- Any TEAE
- Any drug-related TEAE
- Any severe TEAE
- Any serious TEAE

- Any serious drug-related TEAE
- Any TEAE leading to drug interruption
- Any TEAE leading to drug withdrawal
- Any TEAE leading to death

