### **12.3. Clinical Laboratory Evaluations**

The following protocol-specified parameters from the central laboratory will be summarized:

- Hematology panel will include: complete blood count (CBC) with differential, including red blood cell (RBC) count, hemoglobin, hematocrit, mean corpuscular hemoglobin (MCH), mean corpuscular hemoglobin concentration (MCHC), mean corpuscular volume (MCV), white blood cell (WBC) count (with differential), and platelet count.
- Serum chemistry panel will include: total protein, albumin, calcium, phosphorous, glucose, total cholesterol, triglycerides, uric acid, total bilirubin, alkaline phosphatase, aspartate aminotransferase (AST)/serum glutamic oxaloacetic transaminase (SGOT),

alanine aminotransferase/serum glutamic pyruvic transaminase (SGPT), sodium, potassium, chloride, carbon dioxide, blood urea nitrogen (BUN), creatinine, lactic dehydrogenase (LDH), magnesium.

- Complement activation (Bb, C3a and C5a).
- Coagulation assessment will include: prothrombin time and activated partial thromboplastin time (APTT).
- Urinalysis will include specific gravity and pH,.

Summary statistics of observed values and changes from baseline will be provided by time point (time points include the scheduled visits for labs, the follow-up visit, the end of Weeks 0-12, the end of Weeks 12-52, and the end of Weeks 0-52).

Frequency summaries (shift tables) of shifts from baseline to post-baseline time points (time points include the scheduled visits for labs, the end of Weeks 0-12, the end of Weeks 12-52, the end of Weeks 0-52, and the worst value of Weeks 0-52) by category of low/normal/high/both low and high (the last category for the shift to the worst value only) will be provided for hematology and serum chemistry.

A summary of laboratory marked abnormalities as defined in Section 18.4 will be provided for Weeks 0-52.

A separate summary of laboratory marked abnormalities will also be presented by normal baseline and abnormal baseline.

A subject data listing of all laboratory data (including urinalysis) will be provided.

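### Laboratory marked abnormalities are summarised for Weeks 0-52 only in the readable SAP, so an unadjusted percentage would depend on how long each arm stays in the study; a Weeks 0-12 table should be added

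*SAP*

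**What the plan says.** SAP 12.3 sets the window for the marked-abnormality table: "A summary of laboratory marked abnormalities as defined in Section 18.4 will be provided for Weeks 0-52". A second table follows with no window stated: "A separate summary of laboratory marked abnormalities will also be presented by normal baseline and abnormal baseline". The shift to worst value is likewise defined over Weeks 0-52 only.

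The same section has other laboratory output. "Summary statistics of observed values and changes from baseline will be provided by time point", including the end of each of the three periods. "Frequency summaries (shift tables) of shifts from baseline to post-baseline time points" cover hematology and serum chemistry at each scheduled visit, at the end of each period and at the worst value. There is also a full listing.

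SAP 5.3.3 fixes who is counted: "At least 1 post-baseline assessment is required for inclusion in the analysis of each specific laboratory, vital sign, weight, or ECG parameter".

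The overall TEAE summary "will be provided for Weeks 0-12, Weeks 12-52, and Weeks 0-52" (SAP 12.2.1). The summaries of all, drug-related and serious TEAEs, and of TEAEs leading to drug withdrawal, use the same three windows (SAP 12.2.2, 12.2.3, 12.2.5, 12.2.6).

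**The concern.** A table of subjects who ever had a marked abnormality gives each subject as many chances as there are blood draws. Early escape opens at the Week 12 Visit (Protocol 3.1), so the number of draws can differ widely between subjects. One post-baseline value is enough to put a subject in the Weeks 0-52 denominator.

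All three GED-0301 regimens take 160 mg QD to Week 12 and are pooled for the 12-week efficacy comparison. Weeks 0-12, before escape opens, is therefore the natural period for comparing 160 mg QD with placebo on laboratory safety. The readable plan has no marked-abnormality table for it.

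Clinically significant laboratory change is a named safety endpoint (SAP Table 3). Safety is reported without tests, so readers will compare the percentages directly.

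**Working it through.** The documents state no marked-abnormality rate and no dropout rate, so there is no planned figure to reproduce. The check has two parts: count the draws, then see what an ever/never percentage does when retention differs.

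**Draws (Protocol Table 3)**

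- The "Clinical Lab (Chemistry" row and the coagulation row have scheduled post-baseline draws at Weeks 12, 20, 28, 36, 44 and 52. That is 6 for a completer and 1 for a subject who escapes at Week 12.
- Hematology is drawn every 4 weeks from Week 4 to Week 52. That is 13 for a completer and 3 for a Week 12 escaper.
- Subjects not entering the long-term study also have a Follow-up draw. For them chemistry runs from 2 (leaving at Week 12) to 7. Whether Follow-up values count in Weeks 0-52 cannot be seen, because the time-point text is redacted.

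**Formula**

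Let p be the risk of a marked abnormality per draw, taken as independent and equal in both arms. Let L be the share leaving at Week 12, k the draws of a leaver and n the draws of everyone else.

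Percentage ever abnormal = L × [1 − (1 − p)^k] + (1 − L) × [1 − (1 − p)^n]

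**Chemistry, assumed p = 2%, k = 1, n = 6**

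- Leaver: 1 − 0.98 = 2.00%. Completer: 1 − 0.98^6 = 11.42%.
- Arm with L = 50%: 0.5 × 2.00 + 0.5 × 11.42 = 6.71%.
- Arm with L = 30%: 0.3 × 2.00 + 0.7 × 11.42 = 8.59%.
- Ratio 8.59 / 6.71 = 1.28, with no drug effect.
- Other assumed losses: 40% against 30% gives 8.59 / 7.65 = 1.12; 60% against 20% gives 9.53 / 5.77 = 1.65.

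**Hematology, same p and losses (50% against 30%), k = 3, n = 13**

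- 1 − 0.98^3 = 5.88%; 1 − 0.98^13 = 23.10%.
- Arms: 14.49% and 17.93%; ratio 1.24.

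**Sensitivity of the chemistry ratio (p = 2%, 50% against 30%)**

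| Draws, leaver v others | Arms | Ratio |
|---|---|---|
| 1 v 6, scheduled draws, full completion | 6.71% v 8.59% | 1.28 |
| 2 v 7, with Follow-up draw | 8.58% v 10.42% | 1.22 |
| 1 v 3, shortened follow-up (assumed average) | 3.94% v 4.72% | 1.20 |
| 2 v 4, both | 5.86% v 6.62% | 1.13 |
| Abnormality persistent from first draw | equal | 1.00 |

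The shortened rows matter because the sponsor stopped the study early (SAP 2), so many subjects may not have reached Week 52.

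**Effect of the proposed tables under the same assumptions**

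- Weeks 0-12 chemistry: one scheduled draw each, so 2% against 2%, ratio 1.00 whatever the later loss.
- Weeks 0-52 per 100 subject-years (1 v 6 case): mean time in study is 0.5 × 12 + 0.5 × 52 = 32 weeks and 0.3 × 12 + 0.7 × 52 = 40 weeks. Rates are 6.71 × 52 / 32 = 10.9 and 8.59 × 52 / 40 = 11.2, ratio 1.02.

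**The case against.** The strongest reply is that much of what is asked for already exists. By-visit statistics and shift tables allow comparison at Week 12 and at the end of Weeks 0-12. Clinically significant laboratory findings after the first dose are recorded as adverse events (Protocol 6.5.5), and TEAEs are tabulated by period. TEAEs by maximum severity also have Weeks 0-52 only, so the laboratory table is not a lone exception. All of this is correct, and it lowers the severity. It does not replace the missing table. The shift tables use low/normal/high rather than the marked criteria, and the readable text gives none for coagulation or complement. The adverse event route depends on investigator judgement.

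Several stronger readings are tempting, and the documents do not support them:

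- **That the SAP makes no exposure adjustment.** Section 18.4, the part of Section 12 before 12.2 and a point-estimate item in 12.2 cannot be read. An unadjusted percentage is an inference. Nor is there only one marked-abnormality table, given the split by baseline status.
- **That the protocol predicts heavy placebo loss here.** Protocol 1.3.3 mentions "limited comparative data due to the low number of placebo subjects remaining beyond the 12-week time point", but it is describing placebo-controlled studies in general, to justify the timing of endoscopy. Escape is optional, and no arm-specific loss is given before or after Week 12.
- **That the arm with more loss looks safer by construction.** This requires abnormalities that keep arising over time. There is no distortion if they persist from the first draw.
- **That the table would hide harm from GED-0301.** If placebo loses more, the distortion runs against GED-0301. The early stop should shorten follow-up about equally across randomised arms, so it is not itself a source of imbalance.

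**Conclusion.** The narrow point stands: in the readable text, the marked-abnormality summary and the worst-value shift have no Weeks 0-12 or Weeks 12-52 version, and the number of chances to be counted depends on time in study. An unadjusted Weeks 0-52 percentage would therefore mix drug effect with retention.

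The size cannot be known from the documents. Under the assumed 2% risk per draw and 50% against 30% loss, the spurious chemistry ratio is between about 1.13 and 1.28 depending on Follow-up draws and length of follow-up. It rests on independent draws, equal per-draw risk and loss concentrated at Week 12. No formal conclusion depends on the table, since safety is descriptive. This is a low-severity improvement to a safety comparison, not an error that undermines the analysis.

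**What to change.** In SAP 12.3:

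1. Give the marked-abnormality summary and the shift to worst value for Weeks 0-12 (pooled GED 160 against placebo) and Weeks 12-52, as well as Weeks 0-52.
2. Use as denominator the subjects with at least one post-baseline value of the parameter in that period, and state the statistic reported.
3. For Weeks 12-52 and Weeks 0-52, add an exposure-adjusted rate, for example subjects with an event per 100 subject-years, unless the redacted text already provides one. A Weeks 12-52 percentage alone would still mix unequal follow-up.
4. Base the GED 160 versus placebo statement on laboratory safety on the Weeks 0-12 table.
5. State the window of the table split by baseline status, and whether Follow-up values are included.

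The cost is SAP wording and repeat runs of existing tables, with no new data. The downside is a few more descriptive tables, and chemistry in Weeks 0-12 rests on one scheduled draw, so that table is fair between arms but says nothing about later onset.

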#### **12.4. Vital Signs and Body Weight**

For vital signs and body weight, summary statistics of observed values and changes from baseline (also percent change from baseline for body weight) will be provided by time point (time points include the scheduled visits for vital signs/body weight, the follow-up visit, the end of Weeks 0-12, the end of Weeks 12-52, and the end of Weeks 0-52).

A subject data listing of all vital signs and body weight will be provided.

#### **12.5. Electrocardiogram**

A frequency summary (shift table) of the shift from baseline to the end of Weeks 0-52 in investigator clinical interpretation of ECG (normal; abnormal, not clinically significant; and abnormal, clinically significant) will be provided.

CEL GENE PROPRIETARY INFORMATION

[REDACTED]

CEL GENE PROPRIETARY INFORMATION

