## 6.2. Double-blind Treatment Period

The subject will begin study treatment upon confirmation of eligibility. For all subsequent visits in the Double-blind Treatment Period, an administrative window of  $\pm 3$  days is permitted. The following evaluations will be performed at the frequency specified in Table 3. The evaluations should be performed prior to dosing on the visit day, unless otherwise specified.

- Prior and concomitant procedures
- Prior and concomitant medications
- AE evaluation (continuously assessed)
- Electrocardiogram at the Week 12 and Week 52 Visits
- Contraception education (Section 6.5.6) at the Baseline Visit (Visit 2)
- A local urine pregnancy test will be performed on all FCBP. All local urine pregnancy test kits will be provided by the central laboratory. Urine and serum pregnancy tests should be performed if the FCBP has missed a menstrual period or the contraception method has changed at any time during the study.
- Vital signs and weight
- Complete physical examination (Section 6.5.1) at the Week 12 and Week 52 Visits
- Limited physical examination (Section 6.5.1) at the Baseline Visit, Week 24, and Week 36 Visits

- An abdominal examination to assess for the presence of an abdominal mass for the CDAI calculation will be performed at every visit. (Section 6.5.1)
- Clinical laboratory evaluations
- Subject Daily Diary Assessment
- CDAI assessment
  - Due to the delay in receiving the hematocrit sample results, beginning at the Week 12 Visit and thereafter until the Week 52 Visit, the CDAI score will be evaluated by the site using the hematocrit results from the previous visit.
- Ileocolonoscopy for SES-CD should be performed within the Visit window at Week 12 and Week 52.

[REDACTED]

- Dispense IP: The Principal Investigator (PI), Sub-investigator (Sub-I), or Study Coordinator (SC) should make an effort to witness subjects taking their first dose and record the date and time in the source document record. The IP (four tablets) should be taken QD by the subjects. Subjects will be instructed to take the IP in the morning, 30 minutes before breakfast, with a glass of water, and they will also be instructed to refer to the label for storage instructions.

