### 6.5.2. Electrocardiogram

Subjects will have a 12-lead electrocardiogram (ECG) at the frequency specified in Table 3. Sites are to use their own local ECG machines and the automated ECG readings will be further interpreted by the Investigator by clinically correlating them with the subject's condition. The Investigator's clinical interpretation will be recorded in the eCRF as: normal; abnormal, not clinically significant; or abnormal, clinically significant.

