### **6.5.5. Clinically Significant Abnormal Findings**

Clinically significant abnormal findings (clinical laboratory assessments, physical examination, ECG), with exception to the disease under study (CD), identified prior to first dose of IP will be recorded on the eCRF as medical history; clinically significant findings after the first dose of IP will be recorded as AEs.

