### 9.7. Safety Analysis

Safety and tolerability will be assessed by clinical review of all relevant parameters including treatment-emergent adverse events (TEAEs), laboratory tests, vital signs, weight, and ECGs. No inferential testing for statistical significance will be performed.

TEAEs will be classified using the MedDRA classification system. All TEAEs will be summarized by system organ class, preferred term, severity, and relationship to IP. TEAEs leading to death or to discontinuation from treatment and serious TEAEs will also be tabulated. In the by-subject analysis, a subject having the same event more than once will be counted only once and by greatest severity.

Laboratory, vital signs, weight, and ECG data will be summarized descriptively by time point. In addition, shift tables showing the number of subjects with values low, normal, and high compared to the normal ranges at baseline versus postbaseline will be provided for laboratory tests.

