**Table 3: Protocol-specified Endpoints (Continued)**

Endpoint	Name	Description	Timeframe
	Efficacy	The proportion of subjects with endoscopic response-50 (ER-50), defined as a reduction of at least 50% in the SES-CD compared with baseline, at Week 52	Week 52
	Efficacy	The proportion of subjects who have a clinical response, defined as a decrease from baseline in CDAI $\geq$ 100 points, at Week 12	Week 12
	Efficacy	The proportion of subjects who achieve corticosteroid-free clinical remission (CDAI <150) at Week 52 among subjects receiving oral corticosteroids for CD at baseline	Week 52
	Efficacy	The proportion of subjects achieving sustained clinical remission, defined as a CDAI score < 150 at both Week 12 and Week 52	Week 12 and Week 52
	Efficacy	The proportion of subjects with endoscopic response-25 (ER-25), defined as a reduction of at least 25% from baseline in SES-CD, at Week 12	Week 12
	Efficacy	The proportion of subjects with endoscopic remission, defined as SES-CD $\leq$ 2, at Week 52	Week 52
	Safety	Type, frequency, severity, seriousness, and relationship of AEs to IP	Through Week 52
	Safety	Number of subjects who discontinue IP due to any AE	Through Week 52
	Safety	Clinically significant changes in vital signs, ECGs, and/or laboratory findings	Through Week 52

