#### **12.2.2. All TEAEs**

All TEAEs will be summarized by SOC and PT as well as by PT only (in descending order of subject incidence of the total group combining all 3 GED-0301 treatment regimens) for Weeks 0-12, Weeks 12-52, and Weeks 0-52.

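### The only visible ECG output is one shift table to the end of Weeks 0-52, which falls short of the protocol's commitment to ECG data by time point

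*SAP*

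**What the plan says.** **Endpoint.** SAP Table 3 lists, as a secondary safety endpoint through Week 52, "Clinically significant changes in vital signs, ECGs, and/or laboratory findings".

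**Collection.** Protocol 6.2 schedules an "Electrocardiogram at the Week 12 and Week 52 Visits". The Table of Events adds a screening ECG and an ET ECG. Under Protocol 6.5.2 the investigator's "clinical interpretation will be recorded in the eCRF as: normal; abnormal, not clinically significant; or abnormal, clinically significant".

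**Protocol analysis.** Protocol 9.7 states: "Laboratory, vital signs, weight, and ECG data will be summarized descriptively by time point". The Protocol Summary repeats this.

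**SAP analysis.** The visible text of SAP 12.5 provides "A frequency summary (shift table) of the shift from baseline to the end of Weeks 0-52 in investigator clinical interpretation of ECG", using those three categories. It shows no Week 12 table, no worst-reading table and no ECG listing.

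**AE route.** Protocol 6.5.5 names ECG among the assessments for which "clinically significant findings after the first dose of IP will be recorded as AEs". SAP 12.2.2 then provides: "All TEAEs will be summarized by SOC and PT as well as by PT only", separately for Weeks 0-12, 12-52 and 0-52.

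**The concern.** A table that keeps one reading per subject cannot show a change that appears at one visit and is gone at the next. Here the reading left out would be Week 12, which is the most useful ECG for a pooled comparison. By then all three active arms have been assigned 12 weeks of the same regimen. After Week 12 they diverge in dose and schedule, and two of them alternate with placebo.

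An end-of-period table also combines ECGs taken at different times and in different treatment phases: Week 12 for those who stop there, ET for later leavers, and Week 52 for completers. The early termination of the study makes that mixture more likely. At stake is how fully a named safety endpoint is described. No hypothesis test or efficacy conclusion depends on it.

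**Working it through.** The plan gives no figure to reproduce. The check counts scheduled ECGs and compares the relevant sections.

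**1. Which ECGs exist.** SAP 5.2.2 takes baseline as the last assessment no later than the date of first dose, so the baseline ECG is the screening one. Subjects who stop at Week 12 complete the Week 12 Visit instead of an ET Visit.

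**2. How many enter the table.** Assume that the end of Weeks 0-52 means the last ECG in that period.

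| Subject's course | Scheduled post-baseline ECGs | Used | Unused |
|---|---|---|---|
| Leaves before Week 12, ET ECG done | ET = 1 | 1 | 1 - 1 = 0 |
| Leaves at Week 12 | Week 12 = 1 | 1 | 1 - 1 = 0 |
| Leaves after Week 12, ET ECG done | Week 12 + ET = 2 | 1 | 2 - 1 = 1 (Week 12) |
| Completes Week 52 | Week 12 + Week 52 = 2 | 1 | 2 - 1 = 1 (Week 12) |

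Wherever an ECG goes unused, it is the Week 12 one. A subject who is normal at screening, abnormal at Week 12 and normal at Week 52 is tabulated as normal to normal.

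**3. Whether another output catches it.**

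| Week 12 shift, resolved at a later ECG | ECG shift table | TEAE tables and AE listing |
|---|---|---|
| New, clinically significant | Absent | Should appear (Protocol 6.5.5; SAP 12.2) |
| Abnormal, judged not clinically significant | Absent | Not required to appear |

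The TEAE tables are arranged by SOC and PT. They give no movement between ECG categories and no denominator of subjects with an ECG at that visit.

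**4. How the SAP treats the other safety data.** For hematology and serum chemistry, SAP 12.3 gives shifts at scheduled visits, at the end of Weeks 0-12 and of Weeks 12-52, at "the end of Weeks 0-52, and the worst value of Weeks 0-52". SAP 12.4 summarizes vital signs and weight at scheduled visits, at follow-up and at the three period ends. Both sections add a data listing. The visible ECG text has one period end only.

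**5. Treatment at each ECG.** In Protocol Table 4 all active arms share one regimen up to Week 12. From then on one arm takes a continuous lower dose and the other two alternate active drug with placebo, in 4-week blocks. An ET ECG in an alternating arm can therefore fall in a placebo block.

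**The case against.** The strongest reply is the AE route. The endpoint concerns clinically significant changes, and Protocol 6.5.5 sends exactly those ECG findings to the AE record. SAP 12.2.2 tabulates them for three periods, and SAP Section 12 has every safety table show each regimen, placebo and GED Total. This stands. A reader might infer from SAP 12.5 alone that a clinically significant Week 12 change which later resolves is lost from the trial's safety reporting. The documents do not support that: it is missing from the ECG table but should be in the TEAE tables and the AE listing.

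Other replies have some force:

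- Protocol 9.1 leaves detail to the SAP, and 9.7 promises shift tables only for laboratory tests. True, but 9.7 separately names ECG among the data to be summarized by time point.
- SAP 12.3 counts the end of Weeks 0-52 as a time point, so one ECG time point is literally covered. With two scheduled post-baseline visits, that is a thin reading of the commitment.
- Laboratory data are quantitative, central and frequent, whereas ECG is a local three-category reading taken rarely. This argues against copying every laboratory table. It does not argue against a Week 12 one.
- Redaction limits what can be said. The time-point definitions in SAP 5.2 are blacked out, a redacted block follows SAP 12.5, and several items in SAP Section 16 are hidden. No conclusion can be drawn from the lack of a visible ECG entry in Section 16.

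**Conclusion.** The point holds as a minor reporting correction. The visible ECG plan does not deliver the by-time-point summary in Protocol 9.7. Two gaps remain after full credit for the AE route: a transient Week 12 shift to abnormal but not clinically significant need appear in no visible summary, and there is no visible ECG comparison at Week 12.

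The size is one unused ECG out of two scheduled for each completer, and the same for each later leaver with an ET ECG. Nothing is lost for subjects whose only post-baseline ECG is at Week 12 or ET.

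It would be tempting to turn this into a number of affected subjects by applying an abnormality rate to the planned pooled group. The documents give no such rate, and SAP Section 2 says the trial was terminated early, so the planned size is not a safe base.

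The conclusion assumes that the end of the period means the last ECG, that the redacted text holds no further ECG table, and, for the AE route, that investigators apply 6.5.5 and that the TEAE definition (not visible) covers these events.

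**What to change.** In SAP 12.5, keep the present table and add two:

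1. A shift from baseline to Week 12 in the three interpretation categories, by regimen, for GED Total and for placebo.
2. A shift from baseline to the worst post-baseline interpretation in Weeks 0-52, in the same columns. Say whether ECGs from unscheduled visits count, since Protocol 6.2.1 allows them.

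Separate tables for the end of Weeks 0-12 and of Weeks 12-52 are not needed: with so few scheduled ECGs they would largely repeat the Week 12 table and the existing one.

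The cost is a few lines of SAP text and two more descriptive tables from readings already in the eCRF. Trial conduct, visits and data collection do not change.
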